#### INSTRUCTIONS

Complete each section of the application. Based on the nature of the research being proposed some sections may not apply. Those sections can be marked as N/A. Remember that the IRB is concerned with risks and benefits to the research participant and your responses should clearly reflect these issues. You (the PI) need to retain the most recent protocol document for future revisions. Questions can be addressed to xxx. **PIs are strongly encouraged to complete this application with** words and terms used to describe the protocol is geared towards someone not specialized in the **PI's area of expertise**.

**IRB: 1. Protocol Title**: FP00031876 Learning after hours: Taking social and emotional learning beyond the classroom with physical activity.

#### IRB: 2. Background and Objectives

- 2.1 List the specific aims or research questions in 300 words or less.
- 2.2 Refer to findings relevant to the risks and benefits to participants in the proposed research.
- 2.3 Identify any past studies by ID number that are related to this study. If the work was done elsewhere, indicate the location.

#### TIPS for streamlining the review time:

- ✓ Two paragraphs or less is recommended.
- Do not submit sections of funded grants or similar. The IRB will request additional information, if needed.

#### Response:

2. This project uses the **evidence-based Play On! program to promote social, emotional, and physical health of children** through active and inclusive play. The Play On! program will be **implemented during the after-school enrichment programs** at 14 elementary schools in the xxx School District using a tiered approach that begins with a playground design assessment and a training for after-school coordinators and healthy school staff (recess aides, physical education teachers, and healthy school managers), and extends to include trainings for students to become peer leaders to facilitate active and inclusive play during recess. This 'train the trainer' model allows for great reach as the students attending the 14 after-school programs will spread their knowledge and skills to all students attending the schools during recess.

# **IRB: 3.** Data Use - What are the intended uses of the data generated from this project? Examples include: Dissertation, thesis, undergraduate project, publication/journal article, conferences/presentations, results released to agency, organization, employer, or school. If other, then describe.

#### Response:

Data obtained from this project may be used in presentations/publication/journal articles and will be used as evidence to support future grant applications.

#### IRB: 4. Inclusion and Exclusion Criteria

4.1 List criteria that define who will be included or excluded in your final sample.

Indicate if each of the following special (vulnerable/protected) populations is included or excluded:

- Minors (under 18)
- Adults who are unable to consent (impaired decision-making capacity)
- Prisoners
- Economically or educationally disadvantaged individuals
- 4.2 If not obvious, what is the rationale for the exclusion of special populations?

4.3 What procedures will be used to determine inclusion/exclusion of special populations?

# TIPS for streamlining the review time.

- Research involving only data analyses should only describe variables included in the dataset that will be used.
- ✓ For any research which includes or may likely include children/minors or adults unable to consent, review content [here]
- ✓ For research targeting Native Americans or populations with a high Native American demographic, or on or near tribal lands, review content [here]

For research involving minors on campus, review content [here]

#### Response:

## Inclusion criteria:

Children:

- Children in after school programs in XXX Schools (N=294 students at 14 schools)
- Children range in age from 5-13 (grades Kindergarten to 6th grade)
- We will not include any other special population (adults who are unable to consent, prisoners, or economically/educationally disadvantaged individuals)

Adults (Healthy School Leaders):

- after-school program leaders in xxxc Schools
- Recess Aides in schools with after school programs in xxx Schools
- Active, Healthy & Safe team members in schools with after school programs in xxx
- Healthy School Managers in schools with after school programs in xxx Schools
- Physical Education teachers in schools with after school programs in xxx Schools:
- Principals in schools with after school programs in XXX Schools

# Exclusion criteria:

- Any child without parental permission or assent
- Any adult from the aforementioned categories without a signed informed consent form

Inclusion/exclusion criteria have been previously determined to be appropriate for minors – in this case, school children.

#### **IRB: 5.** Number of Participants

Indicate the total number of individuals you expect to recruit and enroll. For secondary data analyses, the response should reflect the number of cases in the dataset.

#### Response:

We expect to recruit 294 children in grade three to six from 14 schools in xxx School District (about 21 students per school). We expect to recruit about 150 adults (~10 adults per school).

# IRB: 6. Recruitment Methods

- 6.1 Identify who will be doing the recruitment and consenting of participants.
- 6.2 Identify when, where, and how potential participants will be identified, recruited, and consented.
- 6.3 Name materials that will be used (e.g., recruitment materials such as emails, flyers, advertisements, etc.) Please upload each recruitment material as a separate document, Name the document: recruitment methods email/flyer/advertisement dd-mm-yyyy
- 6.4 Describe the procedures relevant to using materials (e.g., consent form).

~

#### Response:

We will recruit all 14 of the after school program schools in xxx Schools to participate in the research. Seven of the schools will receive an intervention in year one and the other seven schools will receive in year two. All schools will participate in assessments during both the fall and spring each year.

We will work with the xxx Schools after school program coordinator to send a recruitment email ( staff\_email\_05.15.22) to the program leaders at the 14 schools. Once the leader agrees to participate, they will send informed consents/assents to parents/guardians of the students in the after school program.

#### IRB: 7. Study Procedures

- 7.1 List research procedure step by step (e.g., interventions, surveys, focus groups, observations, lab procedures, secondary data collection, accessing student or other records for research purposes, and follow-ups). Upload one attachment, dated, with all the materials relevant to this section. Name the document: supporting documents dd-mm-yyyy
- 7.2 For each procedure listed, describe who will be conducting it, where it will be performed, how long is participation in each procedure, and how/what data will be collected in each procedure.
- 7.3 Report the total period and span of time for the procedures (if applicable the timeline for follow ups).
- 7.4 For secondary data analyses, identify if it is a public dataset (please include a weblink where the data will be accessed from, if applicable). If not, describe the contents of the dataset, how it will be accessed, and attach data use agreement(s) if relevant.

#### TIPS for streamlining the review time.

- Ensure that research materials and procedures are explicitly connected to the articulated aims or research questions (from section 2 above).
- In some cases, a table enumerating the name of the measures, corresponding citation (if any), number of items, sources of data, time/wave if a repeated measures design can help the IRB streamline the review time.

#### Response:

We are using a crossover pre/post study design where seven after-school programs would receive the intervention in years 1 and 2 and seven schools would serve as matched comparison sites. During year two, the next seven schools would receive the intervention. This tiered approach begins with an initial assessment of the playgrounds to ensure that designs include the research-based elements of balancing, brachiating, climbing, spinning, sliding, and swinging. During years 1 & 2, Healthy School Staff will be trained with the xxx curriculum and the children will be trained as Peer Leaders (Fall Semesters 2022 and 2023) who are enrolled in the after-school program who then become peer leaders for all children during recess at their school.

Assessments include Physical, Social and Emotional Health Assessments administered fall and spring semesters of both years to track student behaviors. Assessments of the after-school setting will be conducted by Xplore program leaders on paper and include observations of all students attending Xplore programs. Assessments during recess would be conducted by recess aides/healthy school staff and would include a random sample of 25 students at recess. No identifying information will be recorded. Assessments will take approximately 5-10 minutes to complete. A copy of the assessment is included (K-6 Assessment).

We will ask the Healthy School Staff to complete a survey each fall and spring semester to learn about their perceptions of the training and playground activities. The survey will take approximately 5-10 minutes to complete. A copy of the staff assessment is included (Healthy School Staff Survey). Healthy School Staff may also be asked to participate in a 30-minute interview each spring semester.

We will ask students to complete a short survey about their physical, social, and emotional health and perceptions of the play activities in the program twice a year. The survey will take approximately 5-10 minutes to complete. A copy of the student assessment is included (Student Survey).

We will also track student participants' physical activity patterns each semester via accelerometry (total of 4 times) for the 7 intervention schools student participants (n=147), and at the other 7 program schools during their control condition year (n=147). Students will wear ActiGraph GT3X+ accelerometer devices for 24 hours over a period of seven days twice a year. Three members of our research team will visit the after school program to set up the students with devices, and on the following week to collect the devices. Students will initially be shown how to secure the devices using the easy velcro wristband upon arrival at the program in the afternoon by the research team. Participants will wear accelerometers on their wrist to promote greater wear compliance compared to the hip among children. The match-box sized accelerometers are the most commonly used accelerometers in PA research and have been utilized by our research team in studies involving elementary schoolchildren. If a participant loses the accelerometer, they will be asked to immediately inform the front office staff who will inform our research team via email. Each child participant will be assigned a unique unidentifiable number (study ID) which will be linked to a person and used throughout the study.

Students may also be asked to participate in a small group interview for 15 minutes about the changes in their afterschool program at the end of each semester.

The research team will collect attendance, behavioral referral information at the school level without names. As well as demographic information for student participants only (gender, age, race/ethnicity) at all schools from the front office staff at the end of each semester to look for significant relationships between participation in the project and reduced behavior referrals as well as increase attendance. The school district personnel have agreed to the study design and measures. This data will only be collected for participants in this project.

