# https://researchintegrity.asu.edu/human-subjects/special-considerations for more information.

#### Response:

We have incentives for principals, teachers and students.

**Incentives**: Students: \$10 per student per semester x 25 per school x 14 schools

Incentives: Program Leaders: \$50 gift card per leader per semester x 5 per school x 14 schools

Incentives: Healthy School Leaders: \$50 gift card per leader per semester x 5 per school x 14 schools

Note that all participants are participating in both year 1 and 2 either as a comparison or program participant.

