A cluster randomized controlled trial of an after-school playground curriculum intervention to improve children's physical, social, and emotional health: Study protocol for the PLAYground project

NCT ID not yet assigned

Date: June 20, 2022

Statistical Analysis Plan

Data analysis

Intervention effects on the primary trial outcomes (at each follow-up time point) will be assessed using general linear mixed effects models to account for the clustering of individual measurements within schools. These will include fixed effects for treatment group (intervention vs control), time (baseline and follow-up), and interaction term (intervention x time); include school as a random effect; and be adjusted for covariates related to the outcome (eg, student sex, age). Analyses related to physical, social, and emotional health will be performed with the child (nested within a school) as the unit of analysis. Analysis related to attendance and behavioral change will be performed with the school as the level of analysis. Separate analyses will be performed at each follow-up time point. Schools will be included in analyses if they meet at least 80% adherence to the protocol.

Secondary implementation outcomes will be assessed using descriptive statistics for Healthy Staff and Student survey data (appropriateness and feasibility) and data from monthly observations (fidelity and sustainability). Frequencies, means, and standard deviations will be calculated to describe the distributions, measures of central tendency, and dispersion of item responses. Data from Healthy Staff and Student interviews will be analyzed using a matrix analysis to summarize and organize data in alignment with Proctor's dimensions (adherence, exposure/dose, quality of delivery, component differentiation, and participant involvement), and content analysis to identify salient themes for each school, by school-level income, and collectively among intervention school groups. We will utilize a deductive approach, but allow for additional themes to emerge.

Sample size calculation

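### The protocol does not settle whether the first seven schools continue the intervention in year 2, so a year-2 between-arm comparison has no single meaning and is not intervention versus control under either schedule

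*Protocol*

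**What the plan says.** Protocol section 6 (Recruitment Methods): "Seven of the schools will receive an intervention in year one and the other seven schools will receive in year two". The same response adds: "All schools will participate in assessments during both the fall and spring each year".

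Protocol section 7 (Study Procedures) opens with "We are using a crossover pre/post study design" and continues that "seven after-school programs would receive the intervention in years 1 and 2 and seven schools would serve as matched comparison sites". The next sentence reads: "During year two, the next seven schools would receive the intervention". Training of staff and peer leaders is placed in the fall of both years, without saying which schools train in which fall.

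Further on in section 7, accelerometry is planned each semester ("total of 4 times) for the 7 intervention schools student participants (n=147), and at the other 7 program schools during their control condition year").

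Protocol section 8 (Compensation) notes that "all participants are participating in both year 1 and 2 either as a comparison or program participant".

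The SAP (Data analysis) fits a treatment-group factor with two levels, intervention and control, and its interaction with time, in a separate analysis at each follow-up. It does not list the follow-ups or say how group is coded in year 2. Among the descriptive secondary outcomes it includes "data from monthly observations (fidelity and sustainability"), with no further definition of sustainability.

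**The concern.** Sections 6 and 7 appear to give the first seven schools different exposure in the second of two study years. Section 7 also sits badly with its own label, since schools treated in both years do not cross over.

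All schools are assessed in both years and the SAP analyses every follow-up in the same way, so the question reaches the analysis. A year-2 estimate would be reported as intervention versus control although the schools labelled control are by then receiving the intervention. Whether the other arm has stopped or is in its second year would be unknown from the documents. If the schedule is settled only after data are seen, the meaning of the year-2 contrast and of sustainability can be chosen after the fact.

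**Working it through.** No figure in the plan is to be reproduced here. The check sets the passages side by side and counts schools.

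**Step 1. The two schedules.** A is the plain reading of section 6; B is the text of section 7.

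| | First seven, year 1 | First seven, year 2 | Other seven, year 1 | Other seven, year 2 |
|---|---|---|---|---|
| A | on | off | not yet | on |
| B | on | on | not yet | on |

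The schedules differ in one cell only: the first seven schools in year 2.

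**Step 2. School-years of delivery**, out of 14 schools × 2 years = 28.
- A: 7 × 1 + 7 × 1 = 14.
- B: 7 × 2 + 7 × 1 = 21.

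**Step 3. Schools not yet exposed.**
- Year 1: 7 under A and 7 under B. This matches the 7 intervention and 7 control schools in the SAP's sample size calculation.
- Year 2: 0 under A and 0 under B.

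**Step 4. What a year-2 comparison of first seven minus other seven estimates.**
- A: schools past their intervention year against schools in their first year.
- B: schools in their second year against schools in their first year.

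If the SAP's group label follows the starting assignment, the schools called control are receiving the intervention in year 2 under both schedules. If the label follows current status, then under A the schools called control have already had the intervention, and under B there is no control group.

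**Step 5. Does any other passage decide between A and B?**
- Accelerometry (section 7): four occasions in the first seven schools and only the control year in the others. Continuing measurement in the first seven fits B better, but it states when devices are worn, not what is delivered; it could equally be follow-up after delivery ends.
- Crossover label (section 7): fits A.
- Training in both falls (section 7): fits either, since under A the first fall could serve the first seven and the second fall the others.
- Compensation note (section 8): fits either, as it gives no status by year.

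No passage decides it.

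**Step 6. Which outcomes are touched.** The other seven schools have no accelerometry after their control year, which is year 1 under both schedules. There is therefore no concurrent year-2 between-arm accelerometry comparison. The difficulty applies to outcomes collected in all schools in both years. Sustainability would mean persistence after delivery ends under A and continued delivery under B.

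**The case against.** The strongest reply is that there is no contradiction. Section 6 never says that the first seven schools stop. In a recruitment section its sentence can be read as giving start years, and on that reading it agrees with section 7, with the four accelerometry occasions in support. This has force: a one-year schedule is the plain reading of section 6, not an explicit statement. But it leaves the crossover label unexplained, and nothing in the documents tells the reader to prefer it.

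It can also be said that the SAP does not list its follow-ups, that sustainability is secondary and descriptive and would be undefined under any schedule, and that the year-1 comparison is intact. All three points stand and limit the weight of the finding.

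Some stronger readings are tempting but not supported:
- A reader might infer a numerical swing in the year-2 estimate from the SAP's 0.370 (for example -0.37, 0 or +0.37 under full fading, full persistence or doubling). That figure is a minimum detectable effect, not an expected one-year effect, the three scenarios are invented extremes, and they could not apply to accelerometry.
- A reader might infer that section 8 is a third conflicting passage. It is compatible with both schedules.
- A reader might infer that schools will be unable to tell what to deliver, or will deliver differently. Nothing shows that schools work from these passages.
- A reader might infer that some of the first seven would fail the SAP's 80% adherence criterion under one schedule. The SAP does not say how adherence is scored or over what period.

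**Conclusion.** The inconsistency is real and should be fixed, but it is a matter of interpretation in year 2 and does not undermine the main comparison. It concerns what 7 of 14 schools receive in one of two years, a difference of 7 school-years (14 against 21 of 28). The year-1 contrast of 7 treated with 7 untreated schools is the same under both schedules. In year 2 neither schedule supplies the intervention-versus-control contrast that the SAP applies at each follow-up. Reconciling the protocol settles which contrast the year-2 data give, but does not restore an untreated group.

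This rests on two assumptions. First, the SAP's follow-ups include year-2 waves; that is the natural reading of its wording together with fall and spring assessments in both years, but it is not stated. If only year-1 follow-up is meant, the SAP needs only to say so. Second, a school counts as exposed for the whole of its intervention year. The protocol places training in the fall but does not say whether the fall assessment comes before it, so the status of the other seven schools at the fall year-2 wave depends on that order.

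The documents do not show which schedule is intended, and this review takes no view on it.

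**What to change.** **Protocol.** Reconcile section 6, the design paragraph of section 7 and the accelerometry paragraph of section 7 to one explicit statement of what the first seven schools receive in year 2. Drop the crossover label if those schools do not switch.

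**SAP.**
- List the follow-up waves, and restrict the intervention-versus-control effect to year-1 follow-up, the only year with 7 untreated schools.
- Report any year-2 between-arm contrast under a name that matches the reconciled schedule: post-intervention against first year, or second year against first year.
- Define sustainability to match the same schedule.

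Replacing the group label with an on/off or cumulative-years code would add little. In an analysis of a single year-2 wave, planned exposure is fully determined by arm, so the code only renames the contrast; under the section 7 schedule every school is on in year 2.

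**Cost.** Wording changes in the protocol and SAP, with no new data. The downside is that year-2 data would no longer support an intervention-versus-control claim.

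### The SAP title names a cluster randomized trial, but the protocol describes matched comparison schools and requires no random allocation

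*Protocol*

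**What the plan says.** The two documents label the design differently.

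- SAP, title: "A cluster randomized controlled trial of an after-school playground curriculum intervention". Nothing later in the SAP describes an allocation step.
- Protocol, section 7 (Study Procedures), Response: "We are using a crossover pre/post study design where seven after-school programs would receive the intervention in years 1 and 2", while "seven schools would serve as matched comparison sites". It continues: "During year two, the next seven schools would receive the intervention".
- Protocol, section 6 (Recruitment Methods), Response: "Seven of the schools will receive an intervention in year one and the other seven schools will receive in year two". How the two sets of seven are formed is not stated.

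The only random step in the protocol's procedures concerns whom to observe, not which schools start first: the recess assessments "would include a random sample of 25 students at recess".

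For the primary outcomes the SAP specifies a mixed model with a school random effect. "These will include fixed effects for treatment group (intervention vs control), time (baseline and follow-up), and interaction term (intervention x time"). The model is also to "be adjusted for covariates related to the outcome (eg, student sex, age"). No matching variable, pair or other school-level covariate is named.

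**The concern.** In a 14-school study, how schools are assigned decides what the primary comparison can show. If a random draw sets the start year, a difference in change between the groups can be credited to the programme, within sampling error. If people choose the early schools, for instance for staff interest or playground readiness, those schools may have been heading for a different change anyway. Seven schools per arm leave little room to correct that by modelling.

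The SAP's label asserts the first situation, and the protocol's procedures permit the second. Section 3 of the protocol says the data may be published and will support future grant applications, so the label is likely to be carried forward. The analysis model fits neither situation well: it ignores the matching that a paired randomised design would have, and it names no school-level adjustment that a non-randomised comparison would need.

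**Working it through.** The main check is a reading of the allocation statements; no figure in the plan turns on it.

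**1. Is random allocation stated anywhere?** Apart from the SAP title, the word random is used for the students sampled at recess and in a form prompt about participant IDs (protocol section 11.7). Neither document gives sequence generation, concealment, timing of the draw, matching variables, or a rule for forming pairs. The title is the only support for a randomised design.

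**2. Do the protocol's words contradict randomisation?** No. Schools can be matched and then randomised within pairs. Sections 6 and 7 do not say how schools are assigned. The conflict is between a label that requires a random draw and procedures that do not.

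**3. Is it a crossover?** Under section 7 the first seven schools have the programme in years 1 and 2 and the other seven in year 2:

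- First seven: programme, programme.
- Other seven: control, programme.

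No school goes from programme back to control. That is a staggered start, with an untreated arm in year 1 only. Section 6 does not say that the first seven stop after year 1, so it does not supply the missing sequence.

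**4. What would a matching covariate do in the SAP model?** With complete data at baseline and one follow-up, the group-by-time estimate is

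(mean follow-up − mean baseline, intervention) − (mean follow-up − mean baseline, control).

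A time-constant school covariate X entered as a main effect adds the same amount, γX, to a school's baseline and follow-up means. It cancels in each bracket and leaves the estimate unchanged. Only an X-by-time or pair-by-time term can alter it. With incomplete follow-up the cancellation is no longer exact, but a main effect still does not model a difference in trend.

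**5. What does pairing cost?** Treat schools' changes as the replicates.

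- Unpaired: 14 − 2 = 12 degrees of freedom.
- One matching-variable-by-time term: 12 − 1 = 11.
- Fully paired: 7 − 1 = 6.

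For scale, use the SAP's inputs: 147 students per arm, ICC 0.05, 80% power, alpha 0.05 (taken as two-sided). The cluster size is 294/14 = 21.

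- Design effect = 1 + (21 − 1) × 0.05 = 2.0.
- Standard error = sqrt(2 × 2.0/147) = 0.165.
- Detectable effect, normal approximation: (1.960 + 0.842) × 0.165 = 0.462.
- Noncentral t, 12 df: 0.504.
- Noncentral t, 6 df, no precision gain from matching: 0.555.

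The SAP's 0.370 is not reproduced by these inputs. That is a separate matter and neither supports nor weakens this point. The cost of pairing is 0.555/0.504 = 1.10, about a 10% larger detectable effect if matching gains nothing. Matching breaks even if it cuts the variance of the comparison by 1 − (0.504/0.555)², about 18%.

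**The case against.** The strongest reply is that this is an omission, not a contradiction. Matching and randomising are compatible, and the remedy below combines them. The protocol is an ethics application whose prompts concern risk, recruitment, procedures and consent, and none asks how sites are allocated. The SAP's title refers to a study protocol, yet the file holds only the analysis and sample size, so allocation details may exist elsewhere. All 14 schools are recruited and all receive the programme, so the only question is who starts first.

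Most of that stands. A reader might infer that the study is in fact non-randomised. The documents do not support that, because they are silent on assignment. Nor does any sentence make an explicit causal claim; it is implied by the title and by the SAP's reference to intervention effects.

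A reader might also try to put a size on the bias by taking the between-school SD implied by the ICC, sqrt(0.05) = 0.22, and assuming that early-start schools differ by some fraction of it. That does not follow. The ICC describes differences in level, and the group-by-time contrast removes stable level differences. The documents give no between-school variance in trend and no basis for choosing a fraction.

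The SAP's covariate list is open-ended, so school-level covariates are not excluded. They are not planned either, and as main effects they would not help.

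The reply does not remove the mismatch. The form asks for the procedures step by step, and its closing tips ask for consistency across materials. A reader holding both documents still cannot tell which design is being run.

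**Conclusion.** The concern holds in this form: the SAP names a cluster randomized controlled trial, and the protocol as written does not require one. It does not establish that schools were, or will be, allocated by anything other than chance. No bias figure can be attached.

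The consequence is for interpretation, and it arises on either reading. If schools are randomised within matched sets, the protocol omits the step that justifies the title and the SAP model omits the matching. If they are not, the title is wrong and the SAP lacks adjustment for differing school trends. The conclusion rests on the two documents as supplied; an allocation procedure recorded elsewhere would reduce the remedy to stating it here and aligning the model. Because it governs what the primary comparison can show, it should be settled before schools are assigned or, failing that, before any result is reported as randomised.

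**What to change.** **If allocation is still open.** In section 7 of the protocol, state that the 14 schools form seven matched pairs, name the matching variables, and state that a computer-generated random draw within each pair decides which school starts in year 1. Say who makes the draw, when, and how it is concealed until then. In the SAP, carry the matching into the primary model with pair-by-time or matching-variable-by-time terms; main effects alone are not enough. State the school-level degrees of freedom: about 6 if fully paired, 11 with one matching-variable-by-time term.

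**If allocation is already fixed by other means.** Remove the word *randomized* from the SAP title and describe a matched, non-randomised, staggered comparison. Prespecify school-level covariate-by-time adjustment, limited to very few variables with 14 schools, and limit causal conclusions accordingly.

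**In either case.** Reconcile the crossover label with the schedule in section 7, and make sections 6 and 7 agree on what the first seven schools receive in year 2.

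**Cost.** One protocol paragraph, one or two SAP lines, and the new title if needed. Every school still receives the programme. The statistical price is the lost degrees of freedom: a detectable effect up to about 10% larger under full pairing if matching brings no precision. There may be some pressure on the timetable, since peer-leader training begins in Fall 2022. The SAP is dated June 20, 2022 and records no registration number yet, so on those dates the correction could come before both training and registration.
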